6.5.2 Secondary Objectives Analyses

Categorical secondary outcomes will be compared across the study groups with the use of the Cochrane-Mantel_Haenszel test, similar to the primary analysis. Continuous outcomes will be compared using the VanElteren test. Our threshold for statistical significance will be $p<0.05$ for secondary analyses, but given the fact that there will be multiple such analyses we acknowledge that any conclusions from those analyses should be considered hypothesis-generating.

6.5.3 Exploratory Objectives Analyses (if applicable)

A retrospective examination will be performed to assess improvement in the control group before / after intervention as a measurement of contamination. We expect that providers who receive AKI alerts on some patients may be more likely to look for AKI in other patients, potentially diluting the effect of the intervention – this pre/post intervention analysis will help in assessing that level of contamination.

We have specified several subgroups in whom the benefit of an AKI alert may differ from the general population. These groups will be analyzed as secondary and exploratory analyses. They include:

- Surgical patients
- Subjects with baseline creatinine <1.0mg/dl
- Subjects with baseline creatinine <0.5 mg/dl
- Females (due to lower rate of increase in creatinine after AKI)
- African Americans (due to higher rate of increase in creatinine after AKI)
- Elderly subjects (age > 65, age > 70, and age > 75)
- Subjects in an ICU at the time of the alert
- Subjects who enter the study based on relative vs. absolute creatinine criteria vs. both

Finally, as the academic year progresses, new clinicians (such as residents and interns) may become more facile in their ability to recognize AKI, which may attenuate the effect of this intervention. We will model this in exploratory analyses using an intervention-by-time of year interaction term in models of the primary outcome.

6.5.4 Safety

The risks to subjects in these trials is minimal, as the studies randomize them to usual care versus an alert that simply synthesizes data that is already present in the medical record.

Potential risks include:

- Loss of confidentiality, as we will be collecting patient information and data.
 - o Risk mitigation: There is limited risk to the loss of confidentiality, as only de-identified data is being stored for analysis. All data in this study will be stored on a central server within the Clinical and Translational Research Accelerator (CTRA). The server is only accessible from within the Yale intranet (or via VPN remotely) and additionally requires separate logon username and password.

Data abstracted from the medical record (see Appendix A) will be de-identified, with a linking file retained in a separate location that will allow for future linking of de-identified data to protected health information (PHI) for the purpose of potential future studies. Studies that require the use of PHI (for example, linking patient info to national outcomes databases) will require approval of both the manuscript and executive committees and a separate IRB approval. De-identified data will be stored on a secure server, accessed via “dumb” terminals, and all analyses will proceed on that server alone. De-

identified data will be transmitted to outside investigators using secure, encrypted channels upon approval of the manuscript committee.

The study is not causing any novel data to be gathered about any patient; it only gathers data from already-existing electronic health records. No PHI are included in the data being analyzed or published. Study participants therefore face no greater dangers of loss of confidentiality than they already face as patients.

This data is not subject to any data sharing agreements at this time. As this will be a large and useful data set that may be utilized in future research protocols, we plan to maintain both the de-identified data set and the linking dataset for at least the duration of IRB approval, and will seek permission to maintain those files on a yearly basis from the IRB if the research protocol is renewed.

- Overtreatment: If alerts affect physician behavior, then patients randomized to an alert arm may be more likely to undergo certain tests or interventions such as fluid boluses. These interventions fall within the standard-of-care and may benefit patients, but it is also possible that additional interventions may not benefit patients and could incur additional costs.
 - o Risk mitigation: We will educate providers that clinical judgement should supersede any AKI alert. While an order set is an optional action for providers, the order set was designed so as to not promote or increase the use of any one particular therapeutic strategy and includes only benign interventions that can be applied to most patients with AKI.
 - o In addition, we have text on the alert that reads “The clinician that sees the alert and decides to act on it must confirm with the attending the AKI order and subsequent SOC treatment to avoid overtreatment”.
- Inattention to AKI: It is possible that, as providers learn that alerts exist, they become less attentive to the presence of AKI in patients randomized to the usual care group.
 - o Risk mitigation: We limit this risk by including the language “THIS ALERT DOES NOT FIRE FOR ALL PATIENTS WITH AKI” in each alert. Additionally, our educational efforts (which target each hospital division before the trial and periodically after initiation) make explicit the fact that these alerts are being conducted in a randomized framework.
- Alert Fatigue: These studies represent an additional alert to which providers will be exposed and prior research has demonstrated that more frequent alerting may lead to less attention to other alerts.
 - o Risk mitigation: We have given providers an option to stop alerts for particular patients by “Accepting” the alert, which will suppress the alert for a

patient for at least 48 hours. While alert fatigue is a potential risk, this is also a major motivation of this line of research, particularly to develop truly targeted alerts that will only display for those most expected to benefit. Only via randomized trials can truly effective alerts be discovered. Should no effect be found in these studies, it will be advised that AKI alerts should not be continued at the institutions.

- Risk of increased signals of harm in the alert group. Our recent AKI alert trial showed signals of harm of our general AKI alert, as shown by an increased relative risk of the primary outcome, in the two non-teaching hospitals of our study.
 - o Risk mitigation: We specifically designed this study to target those subjects who are expected to benefit most from alerting. We also have purposely included only teaching hospitals in this trial, as they showed no signals of harm in our prior alert study. We plan to perform an interim analysis at 50% enrollment.

6.5.5 Analysis of Subject Characteristics

We will present descriptive statistics as median (interquartile range) for continuous variables and proportions for categorical variables. We will use the Van Elteren test to compare continuous variables across the intervention groups, again accounting for hospital strata.

Statistical significance will be based on a p-value of <0.05.

6.5.6 Interim Analysis (if applicable)

We plan to do three interim analyses, and guidelines will be given to the DSMB for stopping the trial for efficacy, harm, and futility. Our interim analyses will be conducted as follows:

The interim analyses will be performed at 25%, 50%, and 75% enrollment. At the first interim analysis, the trial will stop for efficacy if the p-value is < .0016. At the second interim analysis, the trial will stop for efficacy or futility if the p-value is < .0048 or > .72 and < .014 and > .22 for the third interim analysis. The p-value threshold for the final analysis of the primary outcome is set at <0.044.

6.5.7 Handling of Missing Data

Patients discharged prior to 14 days without an outcome of interest will be assumed to be free of that outcome at 14 days. Death will be treated as a censoring event in analyses where death was not the outcome.

7 Trial Administration

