5.2.2 Secondary Outcome Variables (if applicable)

Secondary outcomes will assess individual components of the primary outcomes, as well as a variety of AKI best practice metrics. Secondary outcomes include:

- 14 day mortality (proportion of patients who expire within 14 days of randomization, assessed from point of randomization to date of death from any cause within 14 days of randomization)
- Inpatient mortality (assessed from point of randomization to date of death from any cause)
- 14-day dialysis (proportion of patients who receive dialysis, assessed from point of randomization to date of first documented dialysis order, within 14 days of randomization)
- Inpatient dialysis (assess from point of randomization to date of first documented dialysis order during index hospitalization)
- Discharge on dialysis (assessed as active orders for dialysis at point of discharge from index hospitalization)
- Progression to stage 2 AKI (assessed as a doubling of serum creatinine from the date of randomization to 14 days post randomization)
- Progression to stage 3 AKI (assessed as a tripling of serum creatinine from the date of randomization to 14 days post randomization)
- Duration of AKI (defined as the time in hours between AKI onset and AKI cessation during index hospitalization)
- 30 day readmission rate
- Index hospitalization cost (assessed from point of randomization to date of discharge from index hospitalization)
- Chart documentation of AKI (assessed by post-discharge ICD-10 codes)
- Proportion of best practices achieved per subject during index hospitalization, to include:
 - o Contrast administration
 - o Fluid administration
 - o Aminoglycoside administration
 - o NSAID administration/cessation
 - o ACE inhibitor administration/cessation
 - o Urinalysis order
 - o Documentation of AKI
 - o Monitoring of creatinine

- Monitoring of urine output
- Renal consult

Each metric above is binary and the outcome is reported as a composite best practice outcome representing the proportion of best practices achieved per subject.

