6.5 Planned Analyses

6.5.1 Primary Objective Analysis

For the primary analysis, and all comparisons of categorical variables between the intervention and control group, we will use the Mantel-Haenszel test, accounting for each hospital site as an individual stratum. The Mantel-Haenszel approach will be used to obtain the pooled relative risks across hospital strata without adjusting for other baseline factors.

The primary analysis will examine the rate of the primary outcome in groups defined by whether the individual was randomized to “as recommended” vs. “anti-recommended”. The effect of alert vs control (which is also randomized in this framework) will be considered a secondary outcome.

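### Death is to be censored under tests that cannot censor, and 14-day any-cause mortality has no visible source for deaths after discharge; small effects, secondary outcomes only

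*Combined protocol and SAP*

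**What the plan says.** **Death in non-fatal analyses.** Section 6.5.7: "Death will be treated as a censoring event in analyses where death was not the outcome".

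**Tests.** For the primary analysis and all categorical comparisons, section 6.5.1 states "we will use the Mantel-Haenszel test, accounting for each hospital site as an individual stratum". Section 6.5.2 repeats this for secondary outcomes ("Categorical secondary outcomes will be compared across the study groups with the use of the Cochrane-Mantel_Haenszel test") and adds "Continuous outcomes will be compared using the VanElteren test". It calls conclusions from these analyses hypothesis-generating. No log-rank, Cox, cumulative-incidence or competing-risk method is named. The exploratory models in sections 6.4.1 and 6.5.3 are of the primary outcome, in which death is already an event.

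**AKI duration.** Section 5.2.2: "defined as the time in hours between AKI onset and AKI cessation during index hospitalization".

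**Mortality.** Section 5.2.2 assesses 14-day mortality up to "date of death from any cause within 14 days of randomization" and lists inpatient mortality as a separate item. Section 6.5.7 adds: "Patients discharged prior to 14 days without an outcome of interest will be assumed to be free of that outcome at 14 days". Section 7.7 gives the electronic medical record as the sole data source. Section 7.3 describes linkage to national death databases as a potential future step, and section 6.5.4 requires separate IRB approval for it. The Synopsis and section 5.2.1 restrict the primary component to inpatient death, while sections 2.1 and 5.1 (Study Outcomes) speak of mortality within 14 days.

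**The concern.** A rule that the named tests cannot carry out has to be turned into something else when the analysis is programmed. For a patient who dies, that could mean dropping the patient, stopping the clock at death, counting a non-event, or assigning a worst rank. The plan does not choose.

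AKI duration is the outcome most exposed, because a patient who dies or is discharged before AKI ceases has no defined value. Under stop-the-clock coding, a patient who dies at hour 30 with AKI unresolved ranks better than a survivor who recovers at hour 48. If one arm has more deaths, its durations then look shorter although recovery is no faster.

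The mortality item raises a labelling question. A row headed 14-day any-cause mortality will be read as complete. If deaths after discharge are not captured, they are scored as survival, and the row becomes a subset of inpatient mortality.

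**Working it through.** The documents give no death rates, so every rate below is an assumption. The plan states no figure for this point that could be reproduced.

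**1. Scale for AKI duration.** Section 5.1 (Intervention) says roughly 40% of AKI cases resolve within 24 h. For a lognormal duration with log-SD 1 (assumed), the matching median is 24 / exp(-0.253) = 30.9 h, about 31 h. This is approximate, because that clock starts when the alert is accepted, not at AKI onset. A median of 48 h gives only Φ(ln(24/48)) = Φ(-0.693) = 24% resolved by 24 h, so it serves as the pessimistic case.

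**2. Simulation of AKI duration.** Set-up: 4,092 patients 1:1; four hospital strata (assumed shares 50/25/18/7%); identical recovery times in both arms; death times uniform over 14 days; correlation between slow recovery and death of 0, 0.3 or 0.6; two-sided 5% Van Elteren test. A negative z favours the arm with more deaths. Results for deaths of 8% v 12%, over the three correlations:

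| Coding of death before AKI cessation | Mean z, median 31 h | Mean z, median 48 h | Rejection (nominal 5%) |
|---|---|---|---|
| Stop the clock at death | -0.1 to -0.3 | -0.2 to -0.5 | 5–8% |
| Drop the patient | -0.1 to -0.5 | -0.2 to -0.7 | 5–8% at 31 h, 5–11% at 48 h |
| Longest rank | +0.1 to +0.3 (both medians) | as left | about 6% |

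- At 8% v 10%, the first two codings give z no further from zero than -0.3 (31 h) or -0.4 (48 h), with rejection of 5–7%.
- With equal deaths, mean z is about 0 under every coding.
- The effect is limited because many patients who die recover from AKI first: 78%, 66% and 52% at the 48 h median for the three correlations. Their duration is observed.
- Ranking every death worst, including deaths after recovery, gives z of +2.2, +1.7 and +1.1 (rejection 60%, 39% and 21%) at 48 h. That is a composite of death and duration, so a different estimand.

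**3. Binary non-fatal outcomes.** Dropping patients who die without the event divides each arm's risk by (1 - d), where d is the proportion who die without it. The relative risk of the higher-death arm against the other is multiplied by at most:

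- 8% v 10%: (1 - 0.08) / (1 - 0.10) = 1.022
- 8% v 12%: (1 - 0.08) / (1 - 0.12) = 1.045

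**4. Deaths after discharge.** Let p be in-hospital death by day 14 and f the proportion of the rest who die after discharge by day 14, with every such death missed. Missed deaths = (1 - p) × f × 4,092. Their share of all 14-day deaths = (1 - p)f / [p + (1 - p)f].

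- p = 8%, f = 0.5%: 0.92 × 0.005 × 4,092 = 19 patients; 0.0046 / 0.0846 = 5%.
- p = 8%, f = 3%: 0.92 × 0.03 × 4,092 = 113 patients; 0.0276 / 0.1076 = 26%.
- The same range of f gives 4–18% at p = 12% and 11–42% at p = 4%.

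If the same fraction s is missed in both arms, the observed relative risk is (1 - s)p₁ / [(1 - s)p₂] = p₁ / p₂, so it is unchanged. Precision suffers. For true 14-day mortality of 10%, a 20% relative reduction, 2,046 per arm and alpha 0.05, power falls from 61% with none missed to 45% with 30% missed.

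**The case against.** **On censoring.** The term may be meant loosely. The primary analysis is by intention to treat (section 6.4.1), and section 6.5.2 runs categorical secondary outcomes in a similar way. The natural reading for a binary outcome is then that a patient who dies without the event is a non-event, and the other reading moves the relative risk by 1.05 at most. This stands, and it is why the binary part is minor. It does not help AKI duration, where no value is defined. It is also fair that the longest-rank rule swaps a small negative lean for a small positive one. The evidence calls for a stated rule that does not score death as recovery; the exact rule is a matter of judgement.

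**On mortality.** The contents of Appendix A are not shown. The 30-day readmission outcome shows that some record data after discharge are expected, and the absence of patient follow-up in section 6.3.6 does not bar record extraction. The discharge rule need not override a death recorded in the chart. This stands, so relabelling must be conditional.

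**Stronger readings to resist.** A reader might infer that the primary result is compromised. It is not: the composite counts death as an event, section 5.2.1 limits it to inpatient death, and only the wording elsewhere differs. A reader might infer that excess deaths would be hidden, but mortality is reported in its own right. A reader might infer that post-discharge deaths are certainly missed or that they bias the arm comparison. The visible text shows neither.

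**Conclusion.** The point holds at modest size and is worth correcting because the correction is cheap. Section 6.5.7 states a censoring rule that neither named test can apply, and the most literal workaround for AKI duration scores death as early recovery. The lean is a fraction of one standard error even with a 4-point difference in deaths, which is most of the 4.8-point difference (24% v 19.2%) planned for the whole composite. It vanishes when deaths are similar by arm. The -0.7 extreme needs the longer median, the strongest correlation and dropping of patients together.

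For 14-day mortality, the any-cause definition and the rule for early discharges do not fit together unless a post-discharge death source exists. What is at stake is the absolute rate, its label and its precision. The 5–26% share of missed deaths rests on an assumed 0.5–3% post-discharge death rate with every such death missed. The sample size is unaffected.

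**What to change.** **Censoring.**

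- Delete the sentence in section 6.5.7.
- For binary non-fatal outcomes, keep all randomized patients in the denominator, count death without the event as a non-event, and also report event or death as a separately labelled outcome.
- For AKI duration, fix the rule before unblinding. A patient who recovers and later dies keeps the observed duration. A patient who dies before cessation is not scored as recovered at death. One workable form is the longest rank, with stop-at-death as a sensitivity analysis. Its downside is a small mortality component (z about +0.1 to +0.3 in the setting above).
- For discharge with AKI unresolved, show both extremes (hours to discharge, and longest rank).
- Report the number of unresolved deaths and unresolved discharges per arm.

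**14-day mortality.** If Appendix A contains a post-discharge death source, name it in section 5.2.2 and state how complete it is. If not, label the outcome in-hospital death by day 14; the price is a narrower label. In either case, use the inpatient-death wording of the Synopsis and section 5.2.1 in sections 2.1 and 5.1.

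**Cost.** Protocol and SAP wording, plus programming on data already to be extracted. Section 6.1.4 keeps investigators blinded to the end of the trial period, so the rules can still be set blind. No new data are needed unless the sponsor chooses to link deaths, which section 6.5.4 says needs committee approvals and a separate IRB approval.

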7.1 Ethical Considerations: Informed Consent/Accent and HIPAA Authorization

This study will be conducted in accordance with the ethical principles of the Declaration of Helsinki.

This study will operate under a waiver of informed consent. Due to the nature of the study, it is not feasible to consent subjects, as it would severely contaminate the exposure of interest. Patients randomized to the control arm would need to be told not to inform their provider of their participation in the trial, which would severely compromise the therapeutic relationship. The only way to avoid this would be to obtain informed consent from every patient on admission to the hospital, but given that the incidence of AKI is approximately 15% of admissions, this would be impractical and would be unnecessary for the vast majority of patients. Given that the research proposed presents no more than minimal risk to the subjects, and that no procedures are being performed that require consent outside of the research paradigm, we will request a waiver of consent from the Institutional Review Board.

7.2 Institutional Review Board (IRB) Review

The protocol will be submitted to the IRB for review and approval. Approval of the protocol must be obtained before initiating any research activity. Any change to the protocol or study team will require an approved IRB amendment before implementation. The IRB will determine whether informed consent and HIPAA authorization are required.

The IRB will conduct continuing review at intervals appropriate to the degree of risk, but not less than once per year.

A study closure report will be submitted to the IRB after all research activities have been completed.

Other study events (e.g. data breaches, protocol deviations) will be submitted per Yale's IRB's policies.

7.3 Subject Confidentiality

Subject confidentiality is held in strict trust by the research team. Subject medical record review will be limited to the just the elements needed to complete the study. All data, both patient and provider, will be collected electronically and skimmed from the EHR (see Appendix A for data to be extracted), processed electronically, encrypted, deidentified, and transferred to a secure HIPAA-compliant server with 2-factor authentication for storage and later analysis. Data will not be stored on personal computing devices of any kind and will only be accessible from within the Yale firewall or via VPN. The primary dataset will contain no PHI. We will maintain a separate "linking file" that contains all PHI and will be stored on a separate server to limit the risk of accidental disclosure. The linking file is being maintained for potential future linking to national databases of death and dialysis.

7.4 Deviations/Unanticipated Problems

If the study team becomes aware of an anticipated problem (e.g. data breach, protocol deviation), the event will be reported to the IRB.

A protocol deviation is any noncompliance with the study protocol. The noncompliance may be either on the part of the participant, the investigator, or the study site staff. As a result of deviations, corrective actions are to be developed by the site and implemented promptly.

It is the responsibility of the site investigator to identify and report all protocol deviations at Institutional Review Board (IRB) annual renewal. All deviations must be addressed in study source documents, reported to the study sponsor, and the reviewing IRB per their policies.

Unanticipated problems involving risks to participants or others include, in general, any incident, experience, or outcome that meets all of the following criteria:

- Unexpected in terms of nature, severity, or frequency given (a) the research procedures that are described in the protocol-related documents, such as the Institutional Review Board (IRB)-approved research protocol and informed consent document; and (b) the characteristics of the participant population being studied;
- Related or possibly related to participation in the research (“possibly related” means there is a reasonable possibility that the incident, experience, or outcome may have been caused by the procedures involved in the research); and
- Suggests that the research places participants or others at a greater risk of harm (including physical, psychological, economic, or social harm) than was previously known or recognized.

The investigator will report unanticipated problems (UPs) to the reviewing Institutional Review Board (IRB) and to the study sponsor. The UP report will include the following information:

- Protocol identifying information: protocol title and number, PI's name, and the IRB project number;
- A detailed description of the event, incident, experience, or outcome;
- An explanation of the basis for determining that the event, incident, experience, or outcome represents an UP;
- A description of any changes to the protocol or other corrective actions that have been taken or are proposed in response to the UP.

To satisfy the requirement for prompt reporting, UPs will be reported using the following timeline:

- UPs that are serious adverse events (SAEs) will be reported to the IRB and study sponsor, if applicable within 5 working days in accordance with the investigator becoming aware of the event.
- Any other UP will be reported to the IRB and study sponsor within 10 working days of the investigator becoming aware of the problem.

- All UPs should be reported to appropriate institutional officials (as required by an institution's written reporting procedures), the supporting agency head (or designee), and the Office for Human Research Protections (OHRP) within & [insert timeline in accordance with policy] of the IRB's receipt of the report of the problem from the investigator.

